### **Specific Aim 1.**

#### Comparing the effectiveness of MBRP (n=113) to RP (n=113).

- Hypothesis 1. It is hypothesized that MBRP will demonstrate superior effectiveness, as compared to RP, by reductions in heavy drinking days at the end of treatment (8 weeks) and longer term (20 and 32 weeks) decreases in liver function tests (8, 20, and 32 weeks).

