answer that they have previously had alcohol before will be asked to rate: (1) their frequency of use in the last three months on a 9-point scale ranging from “never” to “every day”, (2) their typical quantity of drinks in one sitting on a 10-point scale ranging from “no drinks” to “more than 20 drinks”, and (3) their frequency of getting drunk when drinking in the past three months on a 5-point scale ranging from “never” to “always.”

- The AUDIT (Saunders, Aasland, Babor, De La Fuente & Grant, 1993) is used to detect less severe problem drinkers and addresses both current problems (problems within the last 3 months) and problems across an individual’s lifetime. The AUDIT consists of ten questions that cover such domains as alcohol consumption, drinking behavior, adverse psychological reactions, and alcohol-related problems.
- Participants will be asked about their engagement in any 12-step programs (Tonigan, Miller & Conners, 1997), psychological services for alcohol and other problems, and use of other self-help materials. At baseline, participants will be asked about lifetime engagement in treatment. Because this study will be recruiting a population of heavy drinkers, it will be important for us to know whether or not any of our participants have previously received treatment for alcohol abuse. In future analyses, this information (e.g., prior treatment history) will be used as a covariate.
- The AUQ (Bohn et al., 1995) will be used to assess craving. The AUQ consists of eight items related to urge drink that are rated on a 7-point Likert scale with the extremes anchored by "Strongly Disagree" and "Strongly Agree." The AUQ has demonstrated internal consistency and reliability.
- The ImpSS (Zuckerman, 1996) consists of 19 items measuring impulsivity and sensation seeking that may predict responses to alcohol and drug problems. The sum of the symptoms endorsed is a proxy measure of dependence.

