### ***Power Analysis:***

#### **Sample Size Requirements.**

Sample size was selected to permit analysis of the hypotheses at a two-tailed alpha of .05 and power level of at least .80 following Cohen (Cohen, 1988). G\*Power 3.0.3 (Erdfelder, Faul, & Buchner, 1996) was utilized for some power calculations, while Monte Carlo simulation strategies formed the basis of our power analysis for the mediational model ([name], Schmiege, & Broaddus, 2007; Mackinnon & Dwyer, 1993).

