### **Power for Specific Aim 1 - Detecting Treatment Effects on Alcohol Use Outcomes.**

The analyses of treatment effects will proceed via random coefficient regression utilizing a 2 (**Treatment**: 8 weeks of MBRP vs. 8 weeks of RP) x 5 (**Time**: Baseline, 4, 8, 20, 32 weeks) mixed general linear model. The primary outcome variable tested will be heavy drinking days (HDD), consistent with previous MBRP trials ([name] et al., 2014). Secondary analyses will explore related outcomes such as drinks per drinking day, scores on the ICS, and liver function tests, with appropriate control of Type I error. In each model, the key effect of interest will be the treatment X time interaction. Given the effect sizes in previous trials (small  $d=.23$  or  $f<.10$  to moderate  $d=.45$  or  $f=.20$ ), we conservatively estimate a small effect size (e.g.,  $f=.10$ ). A mixed model testing the between (treatment) X within (time) subjects interaction with a total of 180 participants (90 per treatment group) will give us well over .90 power, assuming alpha of .05 and a correlation of approximately .50 between repeated assessments. Given that we expect 20% attrition over the course of the trial, we will initially recruit ~226 participants.

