#### ***Data Analysis Plan:***

Analyses will be conducted using SAS Version 9.3 and EQS for Windows Version 5.7b. We will conduct extensive analyses of any attrition encountered in the project to determine bias. However, note that in each of the analyses described herein, we will have the capability of using modern approaches to the handling of missing data (Schafer & Graham, 2002) including full information maximum likelihood (FIML) estimation of missing data within Proc Mixed in SAS and within EQS.

Descriptive analyses. The distributional properties of all continuously scaled variables will be examined for skewness and kurtosis to determine the need for normalizing transformations or for alternations to our analysis plan (i.e., generalized estimating equations in SAS or robust estimation in EQS) prior to the primary analyses.

Pretest equivalence. To confirm the validity of random assignment, pretest equivalence of the two treatment conditions across demographics, drinking history, smoking, and all other baseline measures will be assessed via t-tests on continuous items and  $\chi^2$  tests of categorical items. We will use the Bonferroni approach (Keppel, 1991) to correct for alpha inflation with a familywise alpha of .05. Any variables on which the two groups are unequal at pretest will be covariates in all further analyses.

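### Choosing covariates by Bonferroni-corrected baseline tests leaves the heavy-drinking-days model almost always without a prognostic covariate; fix the adjustment set in advance, including baseline heavy drinking days

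*Combined protocol and SAP*

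**What the plan says.** The paragraph on pretest equivalence in the Data Analysis Plan compares the arms on demographics, drinking history, smoking and all other baseline measures. It uses t-tests and chi-square tests, Bonferroni-corrected to a familywise alpha of .05. The consequence is stated as: "Any variables on which the two groups are unequal at pretest will be covariates in all further analyses".

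The primary model is described under Power for Specific Aim 1 and again under Specific Aim 1 in the Data Analysis Plan. It is a 2 (treatment) by 5 (time) mixed model of HDD with baseline as the first level of time. The treatment-by-time interaction is the key effect. If it is significant, planned contrasts test superiority of MBRP at weeks 8, 20 and 32. No covariate is named, and the design overview describes random assignment without stratification factors.

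Other sections carry their own covariate statements. Under Self-Report Outcome Measures, and again in the instrument table under Procedures, prior treatment history is treated thus: "In future analyses, this information (e.g., prior treatment history) will be used as a covariate". Several scales in the same list are to be covaried for baseline differences only where needed, with no criterion. Sleep, stress, diet and exercise are assigned to the inflammation and epigenetic analyses, head motion to connectivity, and age, gender and diet to the microbiome analysis.

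**The concern.** In a properly randomised trial every baseline null hypothesis is true, so a significance test at baseline can only detect chance. A variable matters for adjustment when it predicts the outcome, and the rule never asks about that. Bonferroni at a familywise .05 selects nothing in at least 95% of trials. In the remainder it selects whichever variable happened to be most imbalanced, prognostic or not, and carries it into every later analysis.

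So the primary analysis is in practice unadjusted, with a small chance of an arbitrary covariate chosen after seeing the data. Two things are at stake in the planned follow-up contrasts: precision that baseline data already in hand would supply, and conditional bias when a prognostic variable is moderately imbalanced but below the threshold.

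**Working it through.** **Inputs from the documents.** Two-sided alpha .05 with target power at least .80 (Sample Size Requirements). Assumed effect f = .10, 180 analysed (90 per arm), five visits, and "a correlation of approximately .50 between repeated assessments" (Power for Specific Aim 1). 113 randomised per arm (Specific Aim 1).

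**Assumptions.** The number of baseline tests k is not stated; I use 20 to 80, with 40 as the central case. I take d = 2f, so f = .10 is d = .20. Correlations with HDD for variables other than baseline HDD are illustrative.

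**1. The plan's own figures.** Noncentral F with λ = f²·N·m/(1 − ρ) = .01 × 180 × 5 / .50 = 18 on 4 and 712 df gives power .942, against the plan's claim of well over .90. Attrition: 180/.80 = 225, against about 226. Both reproduce.

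**2. What the tests can flag.** The standard error of a standardised baseline difference is √(2/113) = .133. The flagging threshold is D* = t(1 − .05/(2k), 224 df) × .133.

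| k | critical t | D* (SD) |
|---|---|---|
| 1 (uncorrected) | 1.97 | .26 |
| 20 | 3.06 | .41 |
| 40 | 3.27 | .435 |
| 80 | 3.47 | .46 |

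The corrected thresholds are 2.0 to 2.3 times d = .20. For a 50% binary factor at k = 40 the threshold is about 21 percentage points.

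**3. How often smaller imbalances occur.** For any one variable, P(|D| > .20) = .133, P(|D| > .25) = .06 (.25/.133 = 1.88), P(|D| > .30) = .024 and P(|D| > .40) = .003. Across 40 variables, about 40 × .133 = 5.3 would exceed .20 SD and about 40 × .024 = 1 would exceed .30 SD.

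**4. Effect on a contrast.** An imbalance D on a variable correlated r with HDD shifts a follow-up difference by r·D.

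- D = .25, r = .5: .125 SD, which is .125/.20 = 63% of d = .20. The plan pairs d = .23 with f below .10; on that pairing f = .10 is at least d = .23 and the ratio is at most .125/.23 = 54%.
- Just below D* at k = 40: .13 SD at r = .3, .22 at r = .5, .30 at r = .7.
- Baseline HDD itself at ρ = .50, just below D*: +.22 SD in a follow-up difference, or −(1 − .50) × .435 = −.22 SD in a change from baseline.

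With baseline HDD adjusted for (analysis of covariance), the simulated conditional bias is .000 to .002 SD.

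**5. Precision.** At r = .5 adjustment multiplies the standard error by √(1 − .25) = .866, so .133 becomes .115 at 113 per arm. Power of one contrast at d = .20:

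| Per arm | Unadjusted follow-up difference | Adjusted for baseline HDD |
|---|---|---|
| 90 | .27 | .34 |
| 113 | .32 | .41 |

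At ρ = .50 a change score has variance 2(1 − .50) = 1, so its power equals the unadjusted column and the gain is the same.

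**6. The interaction.** A baseline variable with the same relation to HDD at all five visits moves all five arm differences equally. The shift cancels in treatment by time. A simulation with complete data, a .25 SD imbalance and r = .5 gave the same interaction estimates and standard errors with and without the covariate.

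**The case against.** The strongest reply is that the key test is the treatment-by-time interaction, and step 6 shows that a main-effect covariate neither corrects nor sharpens it. That stands. Adding age, sex or severity as main effects would do nothing for that test with complete data. It does not dispose of the point, because the plan also tests superiority at weeks 8, 20 and 32, and those contrasts, read as follow-up differences, are affected.

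A second reply is that the .25 SD example would escape an uncorrected .05 test too, since that test flags only above .26 SD. Also true: the fault lies in selecting by significance, and Bonferroni widens the blind region from .26 to .41–.46 SD.

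Four stronger readings are tempting, and the documents do not support them:

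- *Unflagged imbalances could swamp the assumed effect.* At k = 40, reaching d = .20 needs r of about .46 together with an imbalance near the threshold. Imbalances above .40 SD occur in about 0.3% of randomisations per variable.
- *The rule contradicts the commitment on prior treatment history.* It says that unequal variables will be covariates, not that only those will be. The two statements are compatible but not aligned.
- *The plan ignores prognostic variables altogether.* It names covariates for the biomarker, connectivity and microbiome analyses. The gap is in the HDD model.
- *Baseline HDD is already dealt with because it is a level of time.* Step 4 shows that this does not remove the bias: a change contrast carries it with the opposite sign.

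**Conclusion.** The point holds in a limited form. Test-based selection will leave the primary HDD model without a prognostic covariate in nearly every realisation of this trial. For the planned follow-up contrasts the cost is conditional bias of the order of .125 SD when a variable correlated .5 with HDD is out of balance by .25 SD, plus forgone power of about 7 to 9 percentage points per contrast from not adjusting for baseline HDD (.27 to .34, .32 to .41).

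A reader might infer that false positives are inflated. Averaged over randomisations they are not. Only conditionally on a bad draw is the error rate raised, for example to about .30 for one contrast when an unadjusted baseline variable with r = .5 is .40 SD out of balance, which is the 0.3% event.

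The thresholds rest on the assumed 20 to 80 tests, the d = .20 benchmark on d = 2f, and the power gain on the plan's own correlation of .50. This is a free improvement rather than a defect that invalidates the primary analysis.

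**What to change.** 1. Delete the rule that makes covariates of variables testing unequal, and report the baseline table by arm without significance tests.
2. Adjust for baseline HDD explicitly, either by analysis of covariance on the follow-up visits with baseline-by-time terms, or by a mixed model that constrains the arms to a common baseline mean. If baseline leaves the outcome vector, restate the overall test that precedes the contrasts: treatment by time would then compare follow-up visits with each other, so a joint test of the treatment effect across those visits is needed.
3. State whether the week 8, 20 and 32 contrasts are follow-up differences or changes from baseline.
4. Name a short fixed set of further covariates already collected, for example age, sex, Alcohol Dependence Scale score and prior treatment history, and say for each whether it interacts with time.
5. Align the covariate wording under Self-Report Outcome Measures and in the instrument table (both the conditional statements and the firm ones) with the Data Analysis Plan models for Aims 1 and 2.

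The cost is wording only. All the variables are already collected and the sample size is unchanged. The changes should be made before outcomes are examined by arm.

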#### **Specific Aim 1 - Detecting Treatment Effects on Drinking Outcomes.**

The effect of the treatment on alcohol use outcomes (HYPOTHESIS 1) will be analyzed with a 2 (**Treatment:** 8 weeks of MBRP vs. 8 weeks of RP) x 5 (**Time:** Baseline, 4, 8, 20, 32 weeks) mixed general linear model with Heavy Drinking Days (HDD) as the primary outcome variable. We will also examine drinks per drinking day, ICS score, and liver function tests as dependent measures in each of 2 additional models, respectively. In the main analysis with HDD, a significant overall test of the treatment X time interaction will be followed by planned contrasts within the mixed model that allow us to test the superiority of MBRP over RP at the 8, 20, and 32 week follow-up points specifically. The FIML estimation procedure implemented in these analyses will allow us to utilize an “intent to treat” approach such that all subjects who are randomized will be included in the analyses (Schafer & Graham, 2002). It may be that the treatments are equally effective on drinking outcomes, and thus we will not see a direct effect of treatment on outcomes. Even in this case, it is possible that the mechanisms through which the treatments had their impact may differ. Thus, tests of Specific Aims 2 and 3 are still important and warranted.

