#### **Specific Aim 2 - Detecting Treatment Effects on Molecular Mechanisms.**

The effect of the treatment on methylation and inflammation (HYPOTHESIS 2) will be analyzed with one 2 (**Treatment:** 8 weeks of MBRP vs. 8 weeks of RP) x 5 (**Time:** Baseline, 4, 8, 20, 32 weeks) mixed multivariate general linear model with methylation outcomes of DRD2, SLC6A3, and DBH and a second model with peripheral inflammation outcomes of IL-6, IL-8, and TNF $\alpha$ . The effect of the treatment on cue-elicited BOLD activation and network connectivity (HYPOTHESIS 3) will be analyzed with a 2-way multivariate analysis of variance (MANOVA; **Treatment:** 8 weeks of MBRP vs. 8 weeks of RP) with BOLD activation in the accumbens, caudate, putamen, and anterior cingulate regions as separate outcomes in the same analysis, and a second MANOVA with network connectivity

The image part with relationship ID rid9 was not found in the file.

in the RECN and LECN as the outcomes. Note, again, that FIML estimation will be used to allow full utilization of available data in an intent to treat framework. It is also possible that the treatments are equally effective on drinking outcomes, and thus we will not see a differential effect of treatment on the mediators. Yet it is still important to know whether levels of methylation or inflammation post-treatment have any impact on changes in

neurocognitive outcomes. Thus, the test of Specific Aim 3 is still critical, even in the case that both treatments are equally effective on both the mediators and drinking outcomes.

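### The primary HDD model fits a separate baseline mean for each arm, so its tests are valid but give up precision that a common baseline mean would recover at no data cost

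*Combined protocol and SAP*

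**What the plan says.** The Specific Aim 1 section of the Data Analysis Plan specifies a treatment (2) by time (5: baseline and weeks 4, 8, 20, 32) mixed general linear model with HDD as primary outcome. The Aim 1 power section adds: "In each model, the key effect of interest will be the treatment X time interaction". If the overall interaction is significant, the plan proceeds to "planned contrasts within the mixed model that allow us to test the superiority of MBRP over RP at the 8, 20, and 32 week" visits.

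The power statement is that "a total of 180 participants (90 per treatment group) will give us well over .90 power". The calculation behind it was made "assuming alpha of .05 and a correlation of approximately .50 between repeated assessments".

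The only route by which baseline HDD could become a covariate is the pretest equivalence paragraph. It compares the arms on the baseline measures, with Bonferroni correction, and carries forward as covariates those found unequal.

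Under Procedures, participants not having an MRI are randomised at the end of the baseline session. Those who are scanned learn their assignment after the first scan, so that all pre-treatment measures come first.

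The plan does not state whether the week-specific contrasts compare levels or changes from baseline, which covariance structure is used, or what shape over time the effect is expected to take. The Hypothesis 2 analyses have the same layout, for example a 2 x 5 "mixed multivariate general linear model with methylation outcomes of DRD2, SLC6A3, and DBH".

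**The concern.** With baseline as a level of time and treatment crossed with time, the model estimates a baseline mean for each arm. Because assignment is random and follows the baseline measures, the true difference between those means is zero. Estimating it anyway has two costs.

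- A week-specific contrast of levels is, with complete data, just the raw difference in means at that visit. The correlation between baseline and follow-up is not used.
- The treatment x time test is a test of changes from baseline, and every change carries the full baseline sampling error.

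HDD is the primary outcome, and the interaction test is the gate to the three contrasts that address Hypothesis 1. Lost precision therefore affects both steps. What is at stake is power, not bias or Type I error.

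**Working it through.** **Inputs from the documents:** "two-tailed alpha of .05 and power level of at least .80"; effect size f=.10 ("we conservatively estimate a small effect size"), with earlier trials cited at d=.23 to .45; 180 evaluable, 90 per arm; correlation .50; five assessments.

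**Assumptions added here:** compound symmetry, complete data, unit variance, time as a factor. The value d=.30 is an illustrative point inside the cited range.

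**1. The plan's own figure.** For a within-between interaction, lambda = f² x N x m / (1 - rho) = .01 x 180 x 5 / .50 = 18. The non-central F with 4 and 712 df gives power .94, consistent with the plan's claim. For attrition, 180 / .80 = 225, against about 226 recruited.

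**2. Week-specific contrasts.** Relative variance for each form:

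- level at the visit: 1.00
- change from baseline: 2(1 - rho) = 1.00
- common baseline mean: 1 - rho² = 0.75

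At rho=.50 both possible codings lose the same 25%, equivalent to needing 1/0.75 = 1.33 times as many participants.

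| d | Power, planned | Power, common baseline |
|---|---|---|
| .23 | .34 | .43 |
| .30 | .52 | .64 |

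**3. Interaction test (4 df).** Let delta be the vector of true arm differences at the five visits.

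- Free baseline means: lambda = (n/2) x sum of (delta_j - mean delta)² / (1 - rho).
- Common baseline mean: lambda = (n/2) x delta_post' V⁻¹ delta_post, with V = R_post - r r'. Here R_post is the correlation matrix of the four post-baseline visits and r their correlations with baseline. At rho=.50, V = .5 I + .25 J and V⁻¹ = 2(I - J/6), where J is the matrix of ones.

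*Equal effect at weeks 4, 8, 20 and 32.* Free: 45 x (.64 + 4 x .04)/.5 x d² = 72d². Common: 45 x 2 x (4 - 16/6) x d² = 120d². Loss: 1 - 72/120 = 40%.

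*Effect only at weeks 8, 20 and 32.* Free: 45 x (2 x .36 + 3 x .16)/.5 x d² = 108d². Common: 45 x 2 x (3 - 9/6) x d² = 135d². Loss: 1 - 108/135 = 20%.

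| Effect shape | d | lambda, free | lambda, common | Power, free | Power, common |
|---|---|---|---|---|---|
| Weeks 4 to 32 equal | .23 | 3.81 | 6.35 | .30 | .49 |
| Weeks 4 to 32 equal | .30 | 6.48 | 10.80 | .50 | .75 |
| Weeks 8, 20, 32 only | .23 | 5.71 | 7.14 | .45 | .55 |
| Weeks 8, 20, 32 only | .30 | 9.72 | 12.15 | .70 | .80 |

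Other shapes at rho=.50 lose 34% (half effect at week 4, full afterwards), 25% (linear by visit), 23% (peak at week 8, then decay) and 17% (linear in weeks).

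**4. Sensitivity.**

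- Correlation: as rho goes from .3 to .7, the loss falls from 56% to 24% for the equal effect and from 32% to 11% for the effect at weeks 8, 20 and 32 only. The common-baseline contrast variance, relative to the level contrast, goes from .91 to .51.
- Dropout: with 113 per arm and 5% lost at each post-baseline visit (20% in total), the contrasts lose 21% to 23% and the equal-effect interaction test 38%.
- Covariance: an AR(1) structure with adjacent correlation .5 or .7 gives interaction losses from 10% to 55%, depending on shape.

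**The case against.** The strongest reply is that nothing is broken. Under randomisation the free-baseline tests are unbiased and hold their size, and the stated power reproduces. On the plan's own metric, an equal post-baseline effect gives .94 as planned and .997 with the change (lambda 18 against 30). This stands, and it makes the point an efficiency recommendation rather than a correction of an error.

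Three stronger readings are tempting, and the documents do not support them.

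- *The interaction test loses 40%.* That needs compound symmetry and an effect already at full size by week 4. The plan states neither, and Hypothesis 1 names only weeks 8, 20 and 32.
- *The contrasts ignore baseline HDD.* This is strictly true only for level contrasts with complete data. The coding is unstated, change contrasts use baseline (inefficiently), and under FIML baseline informs contrasts when later visits are missing. The power section also speaks of random coefficient regression. If time entered as a slope, the 4-df calculation would not apply.
- *The pretest rule cannot bring baseline HDD in.* It can, because HDD is measured at baseline and the rule covers all baseline measures. It would seldom do so: if 20 to 40 measures were tested (an assumption), 113 per arm would need an observed difference of about d=.41 to .43. The plan also does not say how HDD would then serve as both response and covariate.

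**Conclusion.** The concern holds as a loss of efficiency. With time as a factor, the planned HDD model estimates a baseline difference that randomisation makes zero, and no unconditional use of baseline HDD replaces it. At rho=.50, with compound symmetry, 90 per arm and complete data, the cost is 25% of the precision of each week-specific contrast and about 17% to 40% of the interaction test's non-centrality. It changes with the correlation and the covariance structure.

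A reader might infer that this choice explains the low power at d=.23, or that changing it cures that. Neither follows. In the power calculation used, f=.10 corresponds to d=.50 for an equal post-baseline effect (72 x .25 = 18), which is a separate matter. With a common baseline mean, the 4-df power at d=.23 is still only .49 to .55 for the two shapes tabulated. The change should be made because it is an improvement from data already collected, not because the planned analysis is invalid.

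**What to change.** In the Aim 1 power and analysis sections:

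- Fit HDD at all five visits with time as a factor, one baseline mean common to both arms and an unstructured covariance.
- Replace the treatment x time test with the joint test of the four post-baseline arm differences, and take the week 8, 20 and 32 contrasts from the same model.
- State that these contrasts are arm differences at the visit, and that baseline HDD is not subject to the pretest covariate rule.

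All randomised participants with HDD data stay in the likelihood, so the intent-to-treat statement for HDD is unaffected.

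Use the same form for the secondary and Hypothesis 2 models, but among participants who have those measures. The remote procedures collect no blood, so the liver, methylation and cytokine models cannot be described as including everyone randomised.

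The cost is revised wording and a small change to the model code, with no new data. Because this alters the primary test of a trial already under way, record it in a dated amendment before any analysis of outcomes by arm. The safety monitoring section has the principal investigator supply efficacy data for the DSMB's three-monthly reviews, so the amendment should also say what by-arm outcome data had been seen by then.

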### **Overview and Design of the Proposed Study.**

A 2 (Treatment: 8 weeks of MBRP vs. 8 weeks of RP)  $\times$  5 (Time: Baseline, 4, 8, 20, 32 weeks) mixed factorial design, where treatment is a between-subjects factor and time is a within-subjects factor, will be used to test the treatment outcome hypothesis in Aim 1. Subjects will be randomly assigned to receive MBRP or RP for a period of 8 weeks such that there are equal numbers of patients in each group. An intermediate assessment of the effects of treatment on immune system function and epigenetic regulation of dopamine genes will be collected at 4 weeks. Follow-up assessments will be obtained at 8 weeks (the end of treatment), 20 weeks (12 weeks after the end of treatment), and 32 weeks (24 weeks after the end of treatment).

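### The three visit-specific superiority contrasts on heavy drinking days have no stated adjustment or testing order, and the interaction gate alone does not strongly control error across weeks 8, 20 and 32.

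*Combined protocol and SAP*

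**What the plan says.** The design section describes a 2 x "5 (Time: Baseline, 4, 8, 20, 32 weeks) mixed factorial design". The section on power for Specific Aim 1 makes HDD the primary outcome and names the treatment-by-time interaction as the effect of interest. The sample size section works at a "two-tailed alpha of .05 and power level of at least .80".

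In the Data Analysis Plan for Specific Aim 1, a significant overall interaction on HDD leads to planned contrasts within the mixed model, which are to "test the superiority of MBRP over RP at the 8, 20, and 32 week follow-up points specifically". Hypothesis 1 names the same three visits for HDD and does not rank them.

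Multiplicity is addressed for other families:
- secondary Aim 1 outcomes, to be explored "with appropriate control of Type I error", with no method named;
- the baseline equivalence checks, with Bonferroni at a familywise .05;
- exploratory interactions between mechanisms, in the secondary analyses.

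None of these statements reaches the three HDD contrasts.

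**The concern.** The interaction test has 4 degrees of freedom. Rejecting it says that the two arms' time profiles differ somewhere; it does not say where. The trial's clinical claims (better at end of treatment, better at follow-up) come from the contrasts behind it. One overall test followed by three contrasts at full alpha controls the familywise error when every null is true. With three or more contrasts it does not control it when some nulls are true and others false.

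Week 4 makes this sharper. It contributes to the interaction but is neither a contrast nor part of Hypothesis 1 for HDD. A mid-treatment difference that disappears could therefore open the gate with all three claimed visits null. An early effect that fades is also the pattern in which an unsupported claim of lasting benefit would mislead most.

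**Working it through.** **Inputs from the documents.** Two-sided alpha .05; five assessments; allocation "such that there are equal numbers of patients in each group"; analysed sample 180 (90 per arm); "a correlation of approximately .50 between repeated assessments"; effect f = .10, with earlier trials at d = .23 to .45.

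**Inputs assumed.** Normal outcome with SD 1, compound symmetry, complete data, each contrast at two-sided .05, and the effect patterns listed below.

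**Step 1: the plan's own power.** For the interaction, lambda = f² x N x m / (1 - rho) = .01 x 180 x 5 / .5 = 18, on 4 and 712 df. Power is .942, which agrees with the stated figure ("with a total of 180 participants (90 per treatment group) will give us well over .90 power"). For attrition, 180 / .8 = 225, or 113 per arm, which gives 226. Both figures reproduce.

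**Step 2: without the gate.** Three independent tests at .05 give 1 - .95³ = .143, and two give 1 - .95² = .0975. With correlation .5 between contrasts, simulation gives .126 and .091. These are the values approached when the gate is almost certain to open.

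**Step 3: how often the gate opens.** For an effect d at a single visit, the squared deviations of the arm difference from its mean over visits sum to d² x (1 - 1/5). Then lambda = (90/2) x .8d² / .5 = 72d². At d = .45 this is 14.58, and the gate opens in about .88 of simulated trials. At d = .23 it is 3.81, and the gate opens in about .30.

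**Step 4: the plan as written.** The 4-df F test at .05 was simulated as the gate, followed by the three contrasts (at least 20,000 trials per row). The plan does not say whether the contrasts compare arms at the visit or in change from baseline. Both were run, and each range covers the two.

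| True effect at | d | Any false finding, either direction | Same, with Holm |
|---|---|---|---|
| no visit | 0 | .019–.034 | .009–.022 |
| week 4 only | .23 | .057–.081 | .024–.037 |
| week 8 only | .23 | .041–.061 | .019–.030 |
| weeks 4 and 8 | .23 | .052–.072 | .022–.033 |
| week 4 only | .45 | .118–.124 | .044–.045 |
| week 8 only | .45 | .087–.088 | .037–.041 |
| weeks 4 and 8 | .45 | .088–.091 | .041 |
| weeks 4, 8 and 20 | .45 | .047–.049 | .036 |

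With no effect anywhere, the interaction test itself rejects in .049 of trials. Repeat simulations moved these rates slightly: up to about .085 at d = .23, and about .08 to .125 at d = .45 with two or three null visits. At correlations .3 and .7 (visit differences, d = .45), the week-4-only rate is .113 and .111, and the rate for weeks 4 and 8 is .084 at both.

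**Step 5: direction.** A false finding can favour either arm. Counting only those favouring MBRP at d = .45 gives about .055 to .061 for week 4 only and .043 to .046 with two null visits, against a one-direction nominal .025.

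**The case against.** The plan has one primary outcome and one key test, and that test is held at .05. The contrasts are reached only through it. With no effect at any visit, a false contrast finding occurs in only 2% to 3% of trials. A reader might infer that the error rate for the primary outcome is uncontrolled. The documents do not support that: the interaction test is valid, and what is missing is strong control of the visit-specific claims.

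Three further limits stand:
- The plan does not say that the contrasts are unadjusted. It is silent, and testing each at .05 is an inference from that silence.
- It is tempting to quote .126 as the chance of falsely claiming MBRP superior. That figure ignores the gate and counts errors in both directions.
- The largest gated rates need an effect at week 4 that is exactly zero at weeks 8, 20 and 32, at the top of the plan's effect range. At d = .23 the inflation is modest. In the mildest case, half of .041 is about .02, below the one-direction .025. With only one null visit at d = .45, the rate is about .05.

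These limits reduce the size of the problem but do not remove it. Within the plan's own effect range, the error for visit-specific findings can be about double the nominal level, and nothing in the text prevents this. Silence also leaves the choice of adjustment open until the data have been seen.

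**Conclusion.** The concern holds for the visit-specific claims and not for the interaction test. As written, the plan lacks strong familywise control over weeks 8, 20 and 32. When two or three of these visits are null and another visit has a real effect, the chance of at least one false finding in either direction is about .04 to .085 at d = .23 and about .08 to .125 at d = .45. Errors favouring MBRP are about half of these or less, against .025. The figures rest on contrasts at two-sided .05, 90 completers per arm, normality, compound symmetry and correlation near .5, and they depend on the effect pattern. The point is worth correcting because it bears on which visits the trial may claim, and the correction is small.

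**What to change.** In the Data Analysis Plan for Specific Aim 1, keep the significant interaction as the gate and add that the three HDD contrasts (weeks 8, 20 and 32) will be tested by Holm's procedure at a familywise two-sided .05. In every scenario run this held the false-finding rate at about .046 or below (simulation standard error about .0015).

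The cost is per-visit power. It falls from about .76 to .72 for a sustained effect of d = .45, and from about .79 to .70 if only one of the three visits has an effect. The interaction test, its power calculation and the recruitment target of 226 do not change. Replacing the interaction with a single averaged contrast is not needed for this purpose, and it would change the test on which the stated power rests.
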